	
study medication and instructed how to apply it to the exposed area. When the patient first senses the start of developing a cold sore and applies study medication will be considered Day 1. Dosing of the study product will be done five times daily, beginning at the time that a subject first senses the start of the prodromal phase (Day 1). Subjects will be given a diary card to record their pain levels, progression of lesion development and any unusual symptoms (not normally seen with their outbreaks).
 
Patients will be called daily by the study team after their induction visit to determine the start of prodrome. If after 7 days, the patient does not develop any prodromal senses, the patient will be considered an induction failure.
 
When the patient first senses signs or symptoms of a cold sore, they will have the Day 1 visit conducted within 24 hours. Day 1 visit may be conducted in person or as a MyChart Virtual Visit. Their diary card will be reviewed and if they have experienced a prodrome and/or lesion since the induction visit, their compliance with dosing will be checked. If the subject has noted any unusual symptoms, these will be discussed with medical personnel to determine if the symptoms represent a treatment emergent AE. A photo will be taken of the irradiated area (as marked at the induction visit). The blinded assessor will assess the prodrome and/or lesion and take measurements.
 
On Days 3, 5, and 7, the subject will return to the clinic or follow up via virtual video call for assessment of the irradiated area. Study staff will review the subject diary to determine if the subject is correctly noting the lesion stage. Subjects will have a photo taken of the radiated area and asked to continue with dosing as instructed. Any diary card notation of unusual symptoms in subjects will be reviewed by study staff to determine if the symptoms represent a treatment emergent adverse event. The blinded assessor will assess the prodrome and/or lesion and take measurements. More study product may be dispensed as needed. Most subjects' lesions will have resolved by day 7, and they will end study treatment after 7 full days of treatment. If lesion has not resolved by day 7, the maximum number of days the patient may use study drug treatment is 10 days.
 
The EOS is the final study visit will take place on Day 10. A photo will be taken of the irradiated area, the diary card will be carefully reviewed and study product (including empty containers) will be collected. If subjects reach EOS without full resolution of their lesion(s), they will be given the option to begin taking a prn medication for the remainder of the outbreak. Measurements will be taken. If an adverse event has occurred but has not resolved by the EOS visit, the subject will be contacted once weekly and status noted until such time as the event has resolved. The blinded assessor will assess the prodrome and/or lesion.
 
A Safety follow-up phone call will occur 2 days after the EOS to determine if any new AEs have occurred.
 
Safety will also be evaluated by an independent physician throughout the study. The first independent safety evaluation will be done once 5 subjects

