--	--

[figure not shown]
	have reached EOS. Thereafter, the independent safety evaluation will occur as each subsequent group of 5 subjects reaches EOS and will include data on all subjects having reached EOS.
Enrollment Period	Subjects will be enrolled over a 2 year period.
Treatment Period	Subjects will be treated for up to 7 days from the time they first experience a prodrome and/or a lesion. If lesion has not resolved by day 7, the maximum number of days the patient may use study drug treatment is 10 days. If subjects reach EOS without full resolution of their lesion(s), they will be given the option to begin taking a prn standard of care medication for the remainder of the outbreak. Subjects that do not exhibit a prodrome within 7 days of the induction visit, will be considered induction failures and be discharged from the study. Total time of study participation for any given subject may range from 13 to 25 days.
Location	University of Utah MidValley Clinic, Department of Dermatology
Safety Assessments	Solicited AEs by review of diary cards and discussion with subjects
Efficacy Assessments	Primary: 
Number of subjects that experience prodrome (Stage 1) but do not progress to vesicles (Stage 3) by completion of treatment Secondary: 
Subject-assessed duration of painClinician-assessed duration of lesion appearance (Stage 3), as reported by subject, to complete healing (Stage 5)Measurement of cumulative lesion area (all eruptions if more than 1)Measurement of each lesion (if more than one) from eruption (Stage 3) through healing of hard crust (Stage 4) to identify the largest lesion

TABLE OF CONTENTS

PROTOCOL SYNOPSIS	ERROR! BOOKMARK NOT DEFINED.
1. INRODUCTION	1
1.1 Background and Rationale	1
2. OBJECTIVE	2
2.1 Efficacy Endpoints	2
2.1.1 Primary:	2
2.1.2 Secondary:	2
2.2 Safety Endpoint	2
3. STUDY DESIGN	2
4. STUDY TREATMENT	4
4.1 EDTA Eye Drops	Error! Bookmark not defined.
4.2 Comparator: Abreva®	4
4.3 Randomization Codes	4
5. SUBJECT POPULATION	4
5.1 Inclusion Criteria	4
5.2 Exclusion Criteria	5
6. STUDY PROCEDURES	6
6.1 Study Visits	6
6.1.1 Screening Visit (Days -14 to 0)	6
6.1.2 Study Day 1 Visit (Baseline)	Error! Bookmark not defined.
6.1.3 Study Days 3 and 5 Visits	8
6.1.4 Study Day 7 +/- 1 day Visit	8
6.2 Study Day 10 Visit	Error! Bookmark not defined.
6.2.1 End of Study (EOS) Visit	Error! Bookmark not defined.
6.3 Early Discontinuation Visit	9
7. EFFICACY EVALUATIONS	9

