1. INTRODUCTION

1.1 Background and Rationale

Herpes simplex virus (HSV) infections are common and can cause significant morbidity both at the time of the original infection and when recurrences occur. There are two types of HSV – HSV-1 and HSV-2. HSV-1, the most common cause of oral “cold sores,” is transmitted mainly by oral-to-oral contact. Genital herpes is usually caused by HSV-2, although HSV-1 can also cause genital breakouts. Both HSV-1 and HSV-2 infections are lifelong, with the virus living in the ganglia of nerves that supply the area of the original infection and recurring sporadically in the same area of that nerve’s innervation. Most infections and recurrences are asymptomatic, but infectious viral shedding can occur. Patients who are not asymptomatic can develop prodromes of tingling, pain or paresthesia, and eventually blisters and ulcerations with pain. Healing generally occurs within 10 to 19 days after onset in primary infection or within 5 to 10 days in recurrent infection. Lesions usually heal completely, but recurrent lesions at the same site may cause atrophy and scarring.

According to WHO, in 2012 an estimated 3.7 billion people under age 50 (67%) had HSV-1 infection globally. Some patients have predictable outbreaks after exposure to noxious stimuli, such as sunlight fever, menstruation, or stress.

Researchers have found that calcium signaling is involved in the translocation of the virus from the ganglia to the eruption site. It has been found that an increase of calcium levels in the extracellular matrix will precipitate the calcium signaling events that are causal to the migration of the HSV virus from the proximal ganglia to the eruption site. (Hunsperger 2003, Cheshenko 2003) Further, Husperger found in her experiments (in vitro) that the chelation of calcium greatly reduced the reactivation of the HSV virus.

EDTA Eye Drops (EED), which consists of a calcium chelator and a permeation enhancer, could be one such intervention. Livionex has had some anecdotal evidence that this intervention could work at preventing an HSV eruption and post prodromal viral shedding.

IRB-approved clinical studies of HSV-1 have been performed in normal human volunteers with a history of HSV-1, who develop recurrences with prodromes after exposure to UV light. We will use this technique to induce recurrences in susceptible, HSV-1 infected individuals then treat with EED or Comparator 5 times daily.

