3. STUDY DESIGN

This will be a randomized, efficacy assessor-blinded, parallel group, pilot study of up to 20 subjects with documented UV induced herpes labialis. We will enroll until we have 20 subjects that have expressed a lesion from the induction and complete the treatment period of the study. With the possibility of screen failures and induction failures, we may consent up to 35 patients maximum.

Potential subjects will be assessed during a screening visit that must take place no greater than 2 weeks prior to the Induction visit. During the screening period, subjects that meet all other entry criteria will undergo UV susceptibility testing to determine their individual MED (minimal erythema dose). UV susceptibility testing takes place over two days with exposure to UV light on specified regions on the subject's back followed by an assessment of the exposed areas 24 hours later to identify the MED.

Subjects who have a measurable MED will be allowed to enroll in the study. Each subject will be randomly assigned in a 1:1 ratio to receive either EED or Comparator.

Subjects that do not have a measurable MED will be considered screen failures or may have repeat MED testing with new values.

At the Induction Visit, subjects will undergo UV radiation at a level 3 times their MED. The exposed area of the lip will be marked with indelible ink and a baseline photograph may be taken.

Each subject will then be randomly assigned in a 1:1 ratio to receive either EED or Comparator. Subjects will be dispensed study medication and instructed how to apply it to the exposed area. Dosing of the study product will be done 5 times daily, beginning at the time that a subject first senses the start of the prodromal phase (Day 1). The EED is a clear viscous eye drop, and the Comparator is a white cream substance. Therefore, the subject and principal investigator will be unblinded, and only efficacy assessments will be done by a qualified trained blinded assessor.

Subjects will be given a diary card to record their pain levels (starting at Day 1), progression of lesion development and any unusual symptoms (not normally seen with their outbreaks).

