5.1 Inclusion Criteria

To be eligible for enrollment, a subject must meet the following criteria:

1. Understands the requirements of the study and provides written informed consent prior to undergoing any study-related procedures.

2. Subject is a male or female between the ages of 18-80 years old, inclusive.
3. Fitzpatrick skin type II or III.
4. History of at least one year of herpes labialis induced by UV exposure.
5. Able to recall exact location of most common or most recent outbreak.
6. History of at least 50% of cold sore outbreaks occurring with UV (sun) exposure.
7. At least 1 HSV-1 outbreak within the past 12 months.
8. Experiences prodromal symptoms before HSV-1 outbreaks.
9. Subject is willing and able to comply with protocol-specified dosing, visits to the clinic and tracking of pain.

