6.1.3 Day 1 Visit

Day 1 visit will occur within 24 hours of experiencing signs or symptoms of a cold sore. The patient will start applying study drug as soon as they notice signs or symptoms of a cold sore. The subject will present for a follow up appointment in clinic or via virtual video call consisting of:

- Review of the subject's diary card to identify possible treatment emergent adverse events.
- Assessment of the subject's pain on a visual analog scale.
- Measurement of the lesion will be taken (if lesion is present).
- Photographs of area exposed to UV radiation may be asked to be taken by subjects and uploaded into their MyChart account. If patients are present in clinic, photographs will be taken by study staff.
- If the subject has experienced a prodrome or lesion they should have started dosing. The study staff will review their dosing compliance and examine the study product tube/bottle. If the subject is not complying with the dosing regimen, the study staff will determine whether non-compliance is serious enough to warrant terminating the subject's participation. Otherwise, minor non-compliance should be noted, and the subject should be retrained on how to dose themselves.

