10. SCHEDULE OF ASSESSMENTS

ASSESSMENT	SCREENING	Induction Visit	Daily after induction visit to Day 1	DAY 1	DAY 5	DAY 7	DAY 10/ EOS	Follow -up phone call (EOS +2 days)
Informed Consent	X							
Medical/HSV History	X	X (med hx only)						
Urine Pregnancy Test (for woman of child bearing potential only)	X							
Limited Physical Exam	X	X						
Concomitant Medications	X	X						X
UV susceptibility test / MED testing	X (exposure)							
MED Reading		X						
Randomization		X						
UV exposure at 3 x MED (cold sore inducing)		X						
Study Product Dispensed		X						
Dosing Begins				X				
Dosing Ends						X		
Collect Study Product (including empty tubes/bottles)							X	
Photograph of irradiated area and lesion may be taken		X		X	X	X	X	X
Measurement of lesion (if possible)				X	X	X	X	X
Dispensing of Diary Card		X						
Review of Diary Card/Dosing compliance				X	X	X	X	
Solicitation of Adverse Events			X	X	X	X	X	X
Rating of lesion by blinded assessor				X	X	X	X	
Phone call to check for prodromal senses			X

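### The diary's only general symptom item, which triggers adverse-event review, is narrower than the protocol's adverse-event definition, so product-related local symptoms that resemble an outbreak may be missed or attributed to it

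*Combined protocol and SAP*

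**What the plan says.** **Diary content.** The synopsis (Design) has subjects "record their pain levels, progression of lesion development and any unusual symptoms (not normally seen with their outbreaks"). Section 3 gives the same three items and the same restriction: "record their pain levels (starting at Day 1), progression of lesion development and any unusual symptoms (not normally seen with their outbreaks").

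**From diary to AE.** For Days 3, 5 and 7 the synopsis says "Any diary card notation of unusual symptoms in subjects will be reviewed by study staff to determine if the symptoms" are treatment-emergent AEs. The synopsis text for Day 1, and section 3, likewise send noted unusual symptoms to medical personnel. Sections 6.1.3 to 6.1.5 are less specific: staff review the "diary card to identify possible treatment emergent adverse events". Section 6.3 has the follow-up calls ask about unusual symptoms since the last visit.

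**Other routes.** The synopsis (Safety Assessments) lists "Solicited AEs by review of diary cards and discussion with subjects". The schedule in section 10 has a row, "Solicitation of Adverse Events", separate from diary review. It is marked daily between induction and Day 1, at Days 1, 5, 7 and 10/EOS, and at the follow-up call.

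**Population and definition.** Inclusion criterion 8 is "Experiences prodromal symptoms before HSV-1 outbreaks", and section 1.1 says "Patients who are not asymptomatic can develop prodromes of tingling, pain or paresthesia". Section 8.1.1 counts any unfavourable symptom associated in time with use of the product, related or not, and any worsening of a pre-existing condition. Section 8.1.2 requires all AEs after the start of dosing to be recorded.

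**The concern.** The subject is asked to leave out of the symptom field whatever is usual for an outbreak. In this population the protocol itself describes tingling, pain and paresthesia as usual. Dosing begins when the prodrome is first sensed and is applied at the same site, so product sensations and outbreak symptoms overlap from the first dose. A subject who follows the instruction has little reason to write down tingling that the product caused or made worse.

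Safety is half of the stated objective, and AEs are the only safety endpoint. The independent clinician (section 8.2) and the per-subject listings (section 9.3) can show only what was captured. The filter applies to both arms, so the likely effect is an undercount in each, with any true difference in local tolerability shrunk along with it.

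**Working it through.** The plan gives no figure on this point, so the check is mainly a comparison of the text.

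**1. Diary item against AE definition.** The diary item covers symptoms not usual for the subject's outbreaks. Section 8.1.1 covers any unfavourable symptom during use, plus worsening. A usual symptom that worsens after an application falls inside 8.1.1 and outside the diary item. The only expected-progression exclusion in 8.1.1 concerns periodontal disease, so no rule tells staff how to treat expected herpes symptoms.

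**2. Symptom by symptom.**
- *Tingling, paresthesia:* named in section 1.1 as prodromal. They fall outside the diary item by its wording, and no other diary field is described for them.
- *Pain:* recorded daily on a visual analog scale from Day 1 to EOS (section 7.2), so it is not lost. It sits under efficacy evaluations, and no rule says when a rise is assessed as an AE.
- *Burning, stinging:* not named as outbreak symptoms anywhere. They are left out only if the subject regards them as usual.

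**3. Other routes.** Discussion and AE solicitation could pick up all three. No question wording or symptom list is given for either, and no question described links a symptom to an application. The synopsis has the follow-up call ask about any new AEs, whereas section 6.3 asks about unusual symptoms.

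**4. Illustration of size.** The assumptions, none of them from the plan, are:
- 10 subjects on EED, since 20 subjects at 1:1 gives 20/2 = 10; simple randomization may not give exactly 10.
- A true local-reaction rate p.
- A fraction r of affected subjects whose reaction reaches the record by any route.

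The chance of at least one recorded case is 1 − (1 − p·r)^10.

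| p | r = 100% | r = 50% | r = 25% | r = 10% |
|---|---|---|---|---|
| 30% | 1 − 0.70^10 = 97% | 1 − 0.85^10 = 80% | 1 − 0.925^10 = 54% | 1 − 0.97^10 = 26% |
| 20% | 1 − 0.80^10 = 89% | 1 − 0.90^10 = 65% | 1 − 0.95^10 = 40% | 1 − 0.98^10 = 18% |
| 10% | 1 − 0.90^10 = 65% | 1 − 0.95^10 = 40% | 1 − 0.975^10 = 22% | 1 − 0.99^10 = 10% |

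If r is the same in both arms, a true difference p1 − p2 is seen as r·(p1 − p2). The table shows how sensitive a pilot of this size is to r. It does not estimate r.

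**The case against.** The strongest case on the other side is that AE capture does not rest on this diary item alone. Section 10 schedules solicitation apart from diary review, the synopsis adds discussion, and sections 6.1.3 to 6.1.5 review the whole card, pain scale included. The AE definition is broad and nothing in it excludes outbreak-like symptoms. The diary card itself is not in the documents, only a one-sentence description of it, and section 6.1.2 provides for instruction in completing it. Stinging that follows each application could fairly be read as not usual for an outbreak, and so reportable.

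Most of this stands, and it rules out a stronger reading. A reader might infer that the diary asks only for unusual symptoms, that burning, tingling and pain are therefore screened out, and that the expected number of recorded local reactions is near zero. The documents do not support that:
- The diary also records pain and lesion progression.
- Separate AE routes are scheduled.
- A count near zero would require every affected subject to treat the reaction as usual and every other route to yield nothing.

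A reader might also infer that EED is an irritant, or that product pain would distort an efficacy test. The documents call neither product irritating, and section 9.2 names no test for pain.

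The objection does not remove the mismatch. The plan states a filter on the one field it names as the AE trigger, section 6.3 uses similar wording, and the other routes are not described in enough detail to show that they make up for it.

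**Conclusion.** The point holds as a mismatch between the diary and follow-up-call wording and the AE definition in 8.1.1. Product-related tingling, paresthesia or worsened pain at the application site may be missed or attributed to the outbreak. The other routes reduce the risk, and the documents do not allow the remaining under-reporting to be sized.

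The conclusion assumes that the diary card follows its description in the synopsis and section 3, and that a topical product may cause some local symptoms, which the documents do not state. Because the correction is cheap and the trial is small, the change is worth making. It does not put the safety data as a whole in doubt.

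**What to change.** 1. Align the diary description (synopsis and section 3) and the call wording (section 6.3) with 8.1.1: remove the restriction to unusual symptoms for anything that begins or worsens after an application.
2. Add one solicited item to the daily diary and ask it at each visit: new or worse burning, stinging, tingling, itching or redness soon after applying the product (yes/no, severity).
3. In section 9.3, report this item by arm as solicited local tolerability. Judge AE status and relatedness under 8.1.1 rather than coding every yes as an application-site AE. Subjects receive UV at 3 times their MED, and section 6.1.4 itself allows for a UV reaction, so automatic coding would label erythema and prodrome as product reactions.
4. State how a rise on the pain scale is considered for AE assessment.

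The cost is one diary line, one visit question and short text edits. The downside is that some prodrome and UV-reaction symptoms will be recorded in both arms. The reports also come from unblinded subjects (section 3), so a difference between arms in this item needs cautious reading.

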Patients will be called daily by the study team after their induction visit to determine the start of prodrome. When the patient first senses the prodromal phase, they need to be seen within 24 hours for the Day 1 visit. Patients that do not have prodromal senses within 7 days of the induction will be considered induction failures. Induction failure patients will be asked to return their study drug to the study team.

On Days 1, 3, 5, and 7 the subject will follow up in person or via virtual MyChart visit with blinded assessor during which the subject's diary card will be reviewed and compliance with dosing checked. If the subject has noted any unusual symptoms, these will be discussed with medical personnel to determine if a treatment emergent adverse event has occurred or, if the subject has not started treatment, whether their medical history should be updated. If possible, the lesion will be measured. A photo will be taken of the irradiated area (as marked at the induction visit). More study drug may be dispensed as needed. Most subjects' lesions will have resolved by day 7, and they will end study treatment after 7 full days of

treatment. If lesion has not resolved by day 7, the maximum number of days the patient may use study drug treatment is 10 days. An end of study (EOS) visit will occur as soon as their lesion is healed or Day 10, whichever comes first.

The EOS visit (Day 10) is expected to be the final study visit. EOS will occur when a subject's lesion is fully healed or Day 10 (whichever comes first). A photo will be taken of the irradiated area, the diary card will be carefully reviewed and study product (including empty containers) will be collected. Subjects who developed a lesion that has not yet healed will be given the option to begin taking a prn medication that has been previously prescribed to treat an outbreak.

If an adverse event has occurred but has not resolved by the EOS visit, the subject will be contacted once weekly, and status of the AE noted until such time as the event has resolved.

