6.1.4 Study Days 3, 5, and 7 Visits

On Days 3, 5, and 7, the subject will present for a follow up appointment in clinic or via virtual video call consisting of:

- Review of the subject’s diary card to identify possible treatment emergent adverse events.
- Assessment of the subject’s pain on a visual analog scale.
- Measurement of the lesion will be taken (if lesion is present).
- Photographs of area exposed to UV radiation may be asked to be taken by subjects and uploaded into their MyChart account. If patients are present in clinic, photographs will be taken by study staff.
- If the subject has experienced a prodrome or lesion they should have started dosing. The study staff will review their dosing compliance and examine the study product tube/bottle. If the subject is not complying with the dosing regimen, the study staff will determine whether non-compliance is serious enough to warrant terminating the subject’s participation. Otherwise, minor non-compliance should be noted, and the subject should be retrained on how to dose themselves.

Once patients reach the Stage 2/3 lesion their lesion may be swabbed for viral culture (HSV PCR). If the patient reaches Stage 2/3 over the weekend, the lesion will not be swabbed. We will reserve this for the first five patients but may continue to do all patients to ensure lesion is in fact a cold sore and not a reaction to the UV radiation.

6.1.5 EOS – End of Study Visit (Day 10 – or after subject’s lesion has fully healed)

An EOS visit will occur after the subject’s lesion has fully healed or Day 10 (whichever comes first), the subject will present to the clinic for a follow up appointment in clinic or via virtual video call consisting of:

- Review of the subject’s diary card to identify possible treatment emergent adverse events. If the subject has an AE that has not resolved by this time, the site staff will explain to the subject that they will be called every week to check on the status of the AE, until it is resolved.
- Assessment of the subject’s pain on a visual analog scale.

- Photographs of area exposed to UV radiation may be asked to be taken by subjects and uploaded into their MyChart account. If patients are present in clinic, photographs will be taken by study staff.

The subject's diary card and all tubes//bottles of study product (empty, partially used or unused) will be collected and the subject will be released from the study.

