7.2 Subject-assessed duration of pain

Each subject will evaluate their pain daily on a visual analog scale contained in their diary card. They will begin their pain rating on Day 1 and end at their EOS visit.

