8. SAFETY EVALUATIONS

8.1 Adverse Events

8.1.1 Treatment Emergent Adverse Events

An adverse event (AE) or adverse experience is any untoward medical occurrence in a individual who is using the study product and that does not necessarily have a causal relationship with the study product but that occurs after the start of dosing and up to 2 days after the EOS visit. An AE can therefore be any unfavorable and unintended sign, symptom, or disease temporally associated with the use of the study product, whether or not considered related to it. Pre-existing conditions, which increase in frequency or severity or worsen in nature during or as a consequence of use of a drug in human clinical studies, will also be considered as adverse experiences.

An AE **does not** include:

- Medical or surgical procedures (e.g., surgery, endoscopy, tooth extraction, transfusion). The condition that leads to the procedure is the AE.
- Situations where an untoward medical occurrence has not occurred (e.g., hospitalization for elective surgery, social and/or convenience admissions).
- Worsening of symptoms associated with expected progression of periodontal disease are not considered an adverse event in this study

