9. STATISTICAL METHODS

9.1 Analysis Populations

Analysis populations are defined as follows:

- The Safety population will include all subjects who use EED or Abreva for at least one day.
- The Per Protocol population will include all subjects (that were not induction failures) who complete the study, defined as attending all study visits.

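### End of study is Day 10 in the Synopsis but the earlier of healing and Day 10 in Sections 3 and 6.1.5, so pain and adverse-event follow-up can vary with outcome and early healers may literally fail the Per Protocol rule

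*Combined protocol and SAP*

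**What the plan says.** **EOS timing.** The Synopsis (Design) gives a fixed day: "The EOS is the final study visit will take place on Day 10". Section 3 gives a different rule: "An end of study (EOS) visit will occur as soon as their lesion is healed or Day 10, whichever comes first". Section 3 states that rule a second time, and Section 6.1.5 repeats it. The last column of visits in the Section 10 schedule is headed Day 10/EOS, which fits either rule.

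**What happens at EOS.** Under Section 6.1.5 the diary card and all study product "will be collected and the subject will be released from the study".

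**What is tied to EOS.** On pain, Section 7.2 says: "They will begin their pain rating on Day 1 and end at their EOS visit". Section 8.1.1 counts an adverse event if it "occurs after the start of dosing and up to 2 days after the EOS visit". Section 6.3 sets phone calls two and seven days after the final visit; the Synopsis and the schedule show only the two-day call.

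**Visits and analysis set.** Section 6.1.4 reads: "On Days 3, 5, and 7, the subject will present for a follow up appointment in clinic" (or by video), with no exception for a subject already healed. Section 9.1 limits the Per Protocol population to subjects, other than induction failures, "who complete the study, defined as attending all study visits". Section 9.2 does not say which population the efficacy analysis uses. Safety and Per Protocol are the only two defined.

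**The concern.** A site following the Synopsis and a site following Section 3 would observe the same subject for different lengths of time. Under the earlier-of rule, a fast healer supplies fewer pain ratings and has a shorter adverse-event window than a slow healer. If the arms differ in healing, which is what the trial is looking for, they then differ in how long pain and safety are observed.

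The Per Protocol wording adds a second problem. A subject released before Day 7 has no Day 7 visit to attend, so a literal reading removes early healers from the only defined population that resembles an efficacy set. In a trial of about 10 subjects per arm, each exclusion matters.

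**Working it through.** **Inputs**
- Healing of a recurrence takes 5 to 10 days from onset (Section 1.1). I treat these as study days. If onset is counted as day 0, the earliest healing day is 6 and the earliest adverse-event cut-off below is Day 8.
- Most lesions are expected to have resolved by Day 7 (Synopsis, Section 3).
- The target is 20 subjects, randomized 1:1 (Sections 3 and 5).
- Total participation is stated as 13 to 25 days (Synopsis, Treatment Period).

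**The plan's own figure.** Participation = wait from induction to Day 1 + EOS day + follow-up call. With EOS on Day 10, a one-day wait and the two-day call, 1 + 10 + 2 = 13, which matches the stated minimum. With healing on Day 5, 1 + 5 + 2 = 8, which falls below it. The components are not stated, and 25 is not the maximum on the same components (7 + 10 + 2 = 19). So the lower bound fits the Synopsis rule but does not settle the matter.

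**Observation windows.** Adverse-event cut-off = EOS day + 2. Pain is rated from Day 1 to the EOS day.

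| EOS rule | Healing day | EOS day | Pain rated | Adverse events to | Later fixed visits lost |
|---|---|---|---|---|---|
| Synopsis | any | 10 | Days 1–10 | Day 12 | none |
| Sections 3, 6.1.5 | 5 | 5 | Days 1–5 | Day 7 | Days 7, 10 |
| Sections 3, 6.1.5 | 7 | 7 | Days 1–7 | Day 9 | Day 10 |
| Sections 3, 6.1.5 | 10 | 10 | Days 1–10 | Day 12 | none |

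The spread in adverse-event capture is 12 − 7 = 5 days.

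**Primary endpoint window.** The Synopsis (Efficacy Assessments) and Section 7.1 judge Stage 3 by completion of treatment, not by EOS. Product is collected at EOS, however, so an early EOS can also close that window. By stage reached:
- Vesicles have appeared: already a failure, so early release changes nothing.
- A pre-vesicular lesion resolves early: released as a non-progressor, and a later vesicle could be missed. This is the group exposed.
- Prodrome only: there is no lesion to heal, so the trigger is undefined.

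**Per Protocol membership under three readings**
- (a) Days 3, 5, 7 and 10 all required: everyone released before Day 10 fails. If most means more than half of 20, that is at least 11 subjects.
- (b) EOS stands in for Day 10, but Days 3, 5 and 7 are required: subjects released before Day 7 fail. Their number is not given.
- (c) Only visits due up to the subject's own EOS: no one fails.

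**Hypothetical range.** Assume 10 per arm, 4 v 2 non-progressors, and that non-progressors are the ones released early. None excluded: 4/10 v 2/10 (40% v 20%). Half excluded: 2/8 v 1/9 (25% v 11%). All excluded: 0/6 v 0/8. Every count is assumed. The result runs from no change to loss of all successes, so it is not an estimate.

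**The case against.** A reader might infer that a subject whose prodrome settles within a few days is released, counted as a success and never seen again, so that the primary result is biased. The documents do not support that. The trigger is a healed lesion, which a prodrome-only subject does not have; on a literal reading only the Day 10 limb applies to that subject. Subjects with healed vesicles are already failures. Release on Day 3 or 4 would be earlier than the stated 5 to 10 day healing range.

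Nor is a released subject wholly unobserved. Section 6.3 has calls after the final visit with a possible return to clinic, and the schedule marks a photograph and lesion measurement at EOS + 2 days. Stopping at healing does not by itself bias the Kaplan-Meier time to healing, because the event has been reached.

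A reader might also infer that the analysis loses its best responders. That needs the strict reading of attendance and the assumption that efficacy is analysed in the Per Protocol set, which Section 9.2 does not say. Because most lesions are expected to resolve by Day 7, reading (a) could exclude most of the trial and is unlikely to be intended.

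These arguments remove the claim of demonstrated bias in the primary endpoint. They do not remove the conflict. The contacts after release move with EOS: for healing on Day 5 the calls fall on Days 7 and 12, against Days 12 and 17 for EOS on Day 10. The schedule has no blinded rating at EOS + 2, and the adverse-event definition closes before the seven-day call. The benign reading of the Per Protocol rule is reasonable but is not written down.

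**Conclusion.** The inconsistency is real and lies in current text. Its firmest consequence is that, under Sections 3 and 6.1.5, pain and adverse-event windows depend on outcome, with adverse-event capture ending between Day 7 and Day 12 instead of on Day 12 for all. That range rests on the protocol's own healing times read as study days.

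The primary-endpoint consequence is narrower. It concerns mainly subjects whose pre-vesicular lesion resolves early, plus an undefined trigger for prodrome-only subjects. The Per Protocol consequence depends on the reading, from no exclusions to at least 11 of 20. The documents give no early-healing rates by arm, so no size or direction can be put on any effect on the treatment comparison. This should be corrected, but it does not show that the result would be wrong.

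**What to change.** 1. Reconcile the EOS rule across the Synopsis, Section 3, Section 6.1.5 and the schedule, and say how it applies to a subject with prodrome but no lesion.
2. Whichever rule is kept, record Stage 3 status, new lesions, pain and adverse events through one common study day for every treated subject, using the visits already scheduled. A video visit or uploaded photograph is enough, and the protocol already allows both.
3. In Section 9.1, define Per Protocol completion as attending all visits due up to the subject's own EOS.

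The cost is wording plus one or two short virtual checks for early healers; a subject healed on Day 5, for example, would keep Days 7 and 10. The change concerns observation only. The passages on length of treatment also differ (Section 1.1 against Section 3 and the Synopsis Design) and must be reconciled, because the primary window refers to completion of treatment. No view is taken here on what that length should be.
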